### **Deuterium Oxide:**

Formulation; deuterium oxide 10 g / 10 mL presterilized vial or oral syringe with tip cap for enteral administration

Dose and Administration: The vial or syringe volume (10 mL) will be diluted to a final volume of 100 mL with sterile water. Patients will be asked to drink it all, under direct supervision. Details of the procedure for diluting the contents of the syringe and administration method are provided in the laboratory manual.

## **9.3 BLINDING PROCEDURES**

### **9.3.1 Methods of blinding**

To maintain blinding, sotagliflozin and the matching placebo tablets and packaging will be blinded and indistinguishable. During the double-blind Treatment Period for each cohort, each treatment package will be labeled with a number, which is generated by a computer program from Sanofi. Investigators will not have access to the randomization (treatment) code except under circumstances described in [Section 9.3.2](#).

The randomization and the treatment allocation will be performed centrally by an IRT. The study biostatistician provides the randomization scheme to the IRT. Then, the IRT generates the subject randomization list from which it allocates treatment arms to the subject.

Details for the circumstances under which unblinded reports or data will be provided to DMC are provided in the DMC Charter.

### **9.3.2 Randomization code breaking during the study**

In case of an AE, the code should only be broken in circumstances when knowledge of the IMP is required for treating the subject.

Code breaking can be performed at any time by using the proper module of the IRT and/or by calling any other phone number provided by the Sponsor for that purpose. If the blind is broken, the Investigator should document the date, time of day, and reason for code breaking in source data. The identity of the unblinded personnel, how the code was broken, and the treatment kit number should also be recorded. The Sponsor should also be informed. If the code is broken by the Investigator (or other medical doctor in emergency situation), the patient must be withdrawn from IMP administration.

## 9.4 METHOD OF ASSIGNING PATIENTS TO TREATMENT GROUP

The randomized treatment kit number is generated centrally by Sanofi. The IMPs are packaged in accordance with this list.

At the Screening Visit, the Investigator or designee has to contact the IRT to receive the patient number. [REDACTED]

Before randomizing a subject on Day 1, the Investigator or designee should check if patients comply with all inclusion/exclusion criteria. At day 1, the IRT is contacted for randomization and corresponding allocation of treatments package. Patients are randomized to receive either sotagliflozin or placebo, according to the randomization scheme for each Cohort as described below:

Cohort 1: Sotagliflozin 200 mg: Placebo 2:1

Cohort 2: Sotagliflozin 400 mg: Placebo 2:1

Cohort 3 (as amended here): Sotagliflozin 400 mg: Placebo 1:1

For each randomized patient, the IRT will allocate a treatment package number corresponding to the treatment group assigned.

A randomized subject is defined as a subject who is registered and assigned with a treatment kit number from the IRT, as documented in IRT.

A subject cannot be randomized more than once in the study.

A patient can be rescreened once in case of manageable exclusion as deemed by the Investigator. In these cases, a patient will need to sign a new ICF, be registered as a new patient in IRT, and assigned a new patient number in IRT (first Screening Visit is to be registered as a screen failure in IRT), and complete the Screening Visit procedures/assessments again.

Potential replacement patients will have a patient number assigned from IRT and the patient number that is replaced will be recorded in IRT and transferred to the case report form. Each patient will receive the same treatment and treatment sequence as the withdrawn patient. See also [Section 12.3](#).

## 9.5 PACKAGING AND LABELING

Packaging will be undertaken in accordance with the administration schedule. The content of the labeling is in accordance with the local regulatory specifications and requirements.

The appropriate number of packages will be dispensed to cover up to the dispensing visit (please refer to [Section 1.2](#)). Storage conditions and use-by-end date are part of the label text.

Treatment labels will indicate the treatment number (used for treatment allocation and reported in the eCRF).

## 9.6 STORAGE CONDITIONS AND SHELF LIFE

Investigators or other authorized persons (eg, pharmacists) are responsible for storing the IMP/NIMP in a secure and safe place in accordance with local regulations, labeling specifications, policies, and procedures.

Control of IMP/NIMP storage conditions, especially control of temperature (e.g., refrigerated storage) and instructions for handling the Sanofi compound should be managed according to the rules provided by the Sponsor.

The expiry date and storage conditions are written on the IMP/NIMP labels.

The IMP Sotagliflozin 400 mg or sotagliflozin 200 mg or placebo treatment kit should be stored between 15°C and 30°C (59°F and 86°F).

## 9.7 RESPONSIBILITIES

The Investigator, the clinical site pharmacist, or other personnel allowed to store and dispense IMP/NIMP will be responsible for ensuring that the IMP/NIMP used in the clinical trial is securely maintained as specified by the Sponsor and in accordance with the applicable regulatory requirements.

All IMP/NIMP shall be dispensed in accordance with the Investigator's prescription and it is the Investigator's responsibility to ensure that an accurate record of IMP/NIMP issued and returned is maintained.

Any quality issue noticed with the receipt or use of an IMP/NIMP provided by the Sponsor (deficiency in condition, packaging, appearance, pertaining documentation, labeling, expiration date, etc.) should be promptly notified to the Sponsor. Some deficiencies may be recorded through a complaint procedure.

A potential defect in the quality of IMP/NIMP provided by the Sponsor may be subject to initiation of a recall procedure by the Sponsor. In this case, the Investigator will be responsible for promptly addressing any request made by the Sponsor or delegate, in order to recall IMP and eliminate potential hazards.

Under no circumstances will the Investigator supply IMP/NIMP provided by the Sponsor to a third party, allow the IMP provided by the Sponsor to be used other than as directed by this clinical trial protocol, or dispose of IMP in any other manner.

## 9.8 CONCOMITANT MEDICATION

A concomitant medication is any treatment received by the patient concomitantly to any IMP(s). The IMP includes placebo and sotagliflozin 200 mg and 400 mg.

All concomitant medications should be documented on the concomitant medications and herbal therapies page of the e-CRF. This includes all non IMP treatments that are taken by the patients at any time during the clinical study, beginning Day 1.

Additionally, a history of all medications in the 3 months prior to Day 1 should be taken.

An accurate record of all concomitant medications must be entered in the eCRF, including the name of the medication (INN), daily dosage, and duration of use.

Doses of chronically administered medicines should be kept fixed during the trial if at all possible. Special consideration should be given to the following:

### **Digoxin**

A drug interaction study with digoxin, a sensitive P-glycoprotein (P-gp) substrate, indicated that sotagliflozin acts as a weak P-gp inhibitor. Thus, sotagliflozin increases systemic exposure of digoxin. As this study assesses the safety of sotagliflozin for the first time in this patient population, it will have patients with supra-therapeutic levels (defined for the purposes of this study as  $>/= 1.2$  ng/ml) of digoxin at screening excluded from the trial. Patients that require digoxin during the study should have their plasma digoxin levels monitored.

### **Non-steroidal anti-inflammatory drugs (NSAIDs)**

Concomitant use of NSAIDs increases the risk of acute renal injury and re-hospitalization in this patient population (21) and NSAIDs use during treatment for heart failure is contraindicated. Any NSAIDs use during the study would be at the discretion of the Investigator.

### **Anti-hypertensives**

See also [Section 9.12](#). Because sotagliflozin may reduce BP, adjustment of antihypertensive medication may be needed during the study in patients with hypertension, or following discontinuation of treatment with IMP.

### **Anti-diabetic medications**

Sotagliflozin might reduce the need for insulin administration or other relevant medications in diabetic patients. Patients should monitor their blood glucose levels and adjust the dose and/or frequency of administration of relevant medication as required. Please refer to [Section 11.5](#) for the management of hypoglycemic events.

### **Diuretics**

Co-administration of IMP with loop and thiazide diuretics might lead to clinically significant volume depletion.

Modifications to the dose of the loop and/or thiazide diuretic might be necessary. The Investigator should consult with relevant experts (e.g., nephrologists) as appropriate. For patients with a systolic blood pressure  $< 110$  mm Hg at Randomization, the doses of any diuretic or other antihypertensive medication may be decreased in order to prevent possible hypotension.

## 9.9 TREATMENT ACCOUNTABILITY AND COMPLIANCE

Compliance of IMP:

On Days 1 and 14, sotagliflozin will be administered under direct medical supervision, and an appropriate record will be made in the source data by the Investigator or his/her delegate.

Accounting and compliance for IMPs will be performed on, Visit 3 (between day 6 and day 8) and EOT Visit 5 (Day 14 ± 1), or earlier in cases of discontinuation. The Investigator or his/her delegate will check the compliance to the study treatments based on the patient diary and will then complete the appropriate Site treatment and patient treatment log forms. Visual check on returned IMP will be performed by site staff. In addition the dosing information will be recorded on the appropriate pages of the e-CRF.

If compliance is inadequate as determined by the Principal Investigator (PI), patients will be trained again and mentored. If suboptimal compliance continues after training and mentoring, patients may be discontinued at the discretion of the PI after discussion with the Sponsor's medical monitor.

Missed doses of study medication can be made up if taken within 12 hrs. of the regularly scheduled time. Otherwise, the dose should be skipped and patients should take the next scheduled dose at the usual time. Patients with emesis should not take a replacement dose.

### 9.10 PATIENT DIARY

Paper diaries will be used for this study. Information recorded into diary will document the compliance of IMP as well as other safety information (BP, Hypoglycemia, etc) and these recordings will be carefully reviewed also at each visit.

Patients will enter self-reported information starting at Visit 2 into their paper diaries and they will bring it back to the center at each following visit during the treatment and follow-up period). Patients will be instructed how to fill in it every day.

The diary includes sections for recording:

- Date and time of IMP dose
- Any change or new concomitant medication.
- Adverse events, including signs and symptoms suggesting occurrence of hypoglycemia
- Blood Pressure reading

### 9.11 RETURN AND/OR DESTRUCTION OF TREATMENTS

Patients are to return all in use or unused IMP at Visit 5 (or final assessment on-treatment visit in case of permanent premature discontinuation). All partially-used or unused IMPs will be retrieved by the sponsor CRO or delegate. Investigational medicinal product reconciliation must be performed at the site by the Investigator and the monitoring team using treatment log forms and documented on center IMP inventory countersigned by the Investigator and the monitoring team.

A written authorization for destruction will be given by the study team once the IMP reconciliation is achieved. This destruction can be performed at site depending on IMP specificities and local requirements or IMP can be returned to the Sponsor for destruction.

For NIMP not provided by the Sponsor (i.e., metformin or other oral anti-diabetic drugs), tracking and reconciliation is to be undertaken by the Investigator (or pharmacist if appropriate) according to the system proposed by the Sponsor.

## **9.12 POSTSTUDY TREATMENT**

Patients will continue monitoring and recording their BP on a daily basis following discontinuation of IMP. At the follow up telephone check/onsite (only if required by investigator's clinical judgement) visit between day 26 and day 30, the patient will discuss entries in the diary, and any concerns with the investigator or his/her delegate. If, in the opinion of the investigator, the patient needs to attend for further examination and/or investigation, a follow up Visit (Visit 6) will be scheduled to meet the urgency and needs of patient treatment. If no further visit is scheduled, patients will be reminded to return their completed diaries.

## 10 ASSESSMENT OF INVESTIGATIONAL MEDICINAL PRODUCT

### 10.1 ACTIVITY OR PHARMACODYNAMICS

#### 10.1.1 Pharmacodynamic parameters

##### 10.1.1.1 Primary endpoints

- Change in hemoconcentration from baseline to D14 as assessed by changes in hematocrit, hemoglobin, albumin and total protein, based on the assumptions made by Dill and Costill (22)
- Change in plasma volume in milliliters from baseline to D14 as assessed by the indicator dilution method using I-labelled human albumin

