## 5 STUDY OBJECTIVES

### 5.1 PRIMARY

The primary objective of this study is the assessment of safety and tolerability of sotagliflozin, added to the standard of care treatment, in hemodynamically stable patients with worsening of heart failure, compared to placebo.

A co-primary objective of this trial is the estimation of the effect of sotagliflozin, when added to the standard of care treatment, on changes in plasma volume, as assessed by direct (indicator dilution) and/or indirect (hemoconcentration) methods, in hemodynamically stable patients with worsening of heart failure, compared to placebo.

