#### 10.1.2 Assessment methods

All eligible patients will have hemoconcentration samples obtained and total body water (deuterium oxide) assessment performed as per [Section 10.1.2.1](#) below.

Sites that have the capacity to perform the additional plasma volume assessment by the I-albumin method will follow the procedure described in [Section 10.1.2.2](#).

Patients who decline measurement of total body water or plasma volume by the indicator dilution methods, or in cases where in the opinion of the Investigator technical issues might prevent successful completion of those techniques, may still participate in the study provided they have measurements of plasma volume by the indirect hemoconcentration method.

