**10.1.2.1 Hemoconcentration and Total Body Water estimation procedure on Day 1 and Day 14:**

Hemoconcentration will be determined as previously described (22)(23), at all sites.

A new 18 or 20-gauge IV will be placed in a large vein, ideally the antecubital position, on the morning of day 1 and 14. Baseline urine, plasma and serum samples will first be collected.

All patients must have completed the last planned IV bolus or infusion therapy with diuretics.

It is recommended that procedures commence in the morning of D1. The actual start time may vary. The times provided below in Table 3 are indicative.

Total body water measurement, by the deuterium oxide dilution method, will also take place at all sites. Intake of the deuterium oxide solution will take place immediately after completion of the physical exam and baseline specimens at T0 (approximately 7:30 AM). One sample for measurement of deuterium concentration will be collected at baseline and the second one will be collected approximately 3.5 ( ± 10 min) hours after ingestion of the deuterium oxide solution.

At approximately 8 AM the subject will be asked to assume a semi recumbent position that will be comfortable to them for the next one and a half hours. The angle of the bed or chair should be at approximately 45° and will be recorded. At approximately 9:00 AM (after approximately one hour of recumbency) the blood samples for hematocrit, hemoglobin, albumin and total protein will be collected. The arm that the blood samples are being drawn from will not be in a dependent position and will be as close to the level of the right atrium as possible (to prevent hemoconcentration in the arm which can introduce substantial inaccuracy in the measurements).

At approximately 10:00 AM the patient will receive the IMP. At approximately 11:00 AM, a blood sample for deuterium oxide determination will be obtained.

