1.2 OBJECTIVES

1.2.1 Primary objectives

The primary objective of this study is to assess the safety and tolerability of sotagliflozin, added to the standard of care treatment, in hemodynamically stable patients with worsening of heart failure, compared to placebo.

A co-primary objective of this trial is the estimation of the effect of sotagliflozin, when added to the standard of care treatment, on changes in plasma volume, as assessed by direct (indicator dilution) and indirect (hemoconcentration) methods, in hemodynamically stable patients with worsening of heart failure, compared to placebo.

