2.6.1 Description of pharmacodynamic variables

The following pharmacodynamic variables will be analyzed:

Primary PD variables

- Change in hemoconcentration from baseline to D14/EOT as assessed by changes in hematocrit, hemoglobin, albumin and total protein.
- Change in plasma volume in milliliters from baseline to D14/EOT as assessed by the indicator dilution method using ¹³¹I-labelled human albumin.

Secondary PD variables:

- Change in erythropoietin (mU/ml) from baseline to D14 measured by chemiluminescent enzyme-labelled immunometric assay
- Change in NT-proBNP (pg/mL) from baseline to D14 measured by standard electrochemiluminescence immunoassay

Other Exploratory PD endpoints

- Change in total body water (mL) from baseline to D14 as assessed by the indicator dilution method using deuterium oxide
- Change in uric acid (mg/dL) from baseline to 14 days as measured by standard assay
- Change in beta-hydroxybutyrate (μM) from baseline to 14 days as measured by standard enzymatic colorimetric assay
- Change in red cell mass (mL) from baseline to D14, as derived from measurements of plasma volume (assessed by the indicator dilution method using ¹³¹I-labelled human albumin) and hematocrit
- Change in total blood volume (mL) from baseline to 14 days, as assessed by the indicator dilution method using ¹³¹I-labelled human albumin
- Percentage of patients within 15% of ideal blood volume on study day 14
- Blood pressure (sitting, SBP and DBP) at day 14, compared to baseline

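### The SAP gives hemoconcentration no derivation or unit, and its baseline plasma-volume covariate may remove the patients for whom hemoconcentration is the only plasma-volume measure

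*Protocol*

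**What the plan says.** **Objective.** Protocol 5.1 sets as co-primary the estimation of the effect "on changes in plasma volume, as assessed by direct (indicator dilution) and/or indirect (hemoconcentration) methods". SAP 1.2.1 has the same objective, but "as assessed by direct (indicator dilution) and indirect (hemoconcentration) methods".

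**Endpoint and method.** Protocol 10.1.1.1 gives the indirect endpoint as the Day 14 change in hemoconcentration, "as assessed by changes in hematocrit, hemoglobin, albumin and total protein, based on the assumptions made by" the authors of reference 22. Section 10.1.2.1 adds: "Hemoconcentration will be determined as previously described (22)(23), at all sites". By their listed titles, reference 22 concerns calculating percentage changes in plasma and other blood volumes, and reference 23 concerns calculated plasma volume status. Neither document writes out a formula.

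**Who has which measurement.** Under Protocol 10.1.2 the tracer test is done at sites able to do it. Patients who decline it, or for whom it is technically doubtful, "may still participate in the study provided they have measurements of plasma volume by the indirect hemoconcentration method". Protocol 13.1.3.5 adds that a patient with no tracer test on Day 1 need not have one at Visit 5.

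**Analysis.** SAP 2.6.1, in the same words as Protocol 14.7.1, lists "Change in hemoconcentration from baseline to D14/EOT as assessed by changes in hematocrit, hemoglobin, albumin and total protein" and stops there. The tracer variable on the next line has a unit (milliliters); this one has none. SAP 2.6.2 names change in hemoconcentration and change in plasma volume as the main variables. It gives both the same ANCOVA: treatment, diabetic status, ejection-fraction status, and baseline plasma volume as covariate.

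**The concern.** Two gaps meet in one model.

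First, the analysed variable is not defined. The protocol points to a calculated plasma-volume quantity, but the SAP carries forward only a list of four concentrations on different scales. A programmer would have to decide whether change in hemoconcentration means one calculated value, a composite or several models. Nothing says how albumin and total protein enter.

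Second, the covariate is borrowed from the other endpoint. The only baseline plasma volume that the SAP defines is the tracer value. A patient without it cannot enter a complete-case ANCOVA that requires it, even with both hemoconcentration samples in hand. Those are the patients for whom the indirect method is the only route to the co-primary objective. For everyone else, the model adjusts for another variable's baseline and not for the outcome's own.

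**Working it through.** **1. The plan's own figure.** SAP 1.3 states 71% power. Inputs: difference 0.9 x 0.47 = 0.423 L, SD 0.8 L, 54 v 27 patients, one-sided 0.05. The standard error is 0.8 x sqrt(1/54 + 1/27) = 0.1886 L and 0.423/0.1886 = 2.243. Power is 72.5% by the normal approximation and 71.9% by the noncentral t, so the figure reproduces. It concerns completers with plasma volume at both visits. Nothing is sized on hemoconcentration, and this point does not change the 71%.

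**2. The variable, section by section.**
- Protocol 5.1 and SAP 1.2.1: plasma volume, by the indirect method too.
- Protocol 10.1.1.1 and 10.1.2.1: four markers, tied to references 22 and 23.
- Protocol 10.1.2: the indirect method is described as measuring plasma volume.
- Protocol 14.7.1: four markers, with a pointer back to 10.1.1.
- SAP 2.6.1: four markers, no pointer, formula or unit.
- SAP 2.6.2: one named outcome, with number and scale not given.

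**3. Who enters the model.** SAP 2.9 does not replace missing data other than planned baseline values, and gives no method for replacing those. Nothing in the plan therefore supplies a tracer baseline to a patient who never had the test. If m of about 64 patients lack it, the hemoconcentration model keeps 64 - m. With losses spread evenly over the arms, the standard error grows by sqrt(64/(64 - m)). The documents give no m. As assumptions only: m = 0 gives 1.00; m = 16 gives sqrt(64/48) = 1.15; m = 32 gives sqrt(64/32) = 1.41. Apart from precision, the indirect analysis would then include nobody without a direct baseline.

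**4. One derived variable.** Assume that circulating hemoglobin is constant between the two samples. Then BV1 x Hb1 = BV14 x Hb14, so BV14/BV1 = Hb1/Hb14. With PV = BV x (1 - Hct):

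percent change in PV = 100 x [(Hb1/Hb14) x (1 - Hct14)/(1 - Hct1) - 1]

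Illustration: hemoglobin 12.0 to 12.6 g/dL and hematocrit 0.360 to 0.378. 12.0/12.6 = 0.9524; 0.622/0.640 = 0.9719; the product is 0.9256, a fall of 7.4%. Each marker rose by 5% (0.6/12.0 and 0.018/0.360), so a marker change is not itself a plasma-volume change.

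**5. Sensitivity to blood sampling.** If a fraction f of circulating hemoglobin is removed between the samples, the true ratio is (1 - f) times the calculated one. The largest planned draw in Protocol 10.5 is 184.5 mL. SAP 1.3 equates a 10% reduction with 0.47 L, which implies a plasma volume of 4.7 L. At the illustrative hematocrit of 0.360, blood volume is 4.7/0.640 = 7.34 L, so f is at most 0.1845/7.34 = 2.5%. The example becomes 0.9256 x 0.975 = 0.902, a fall of 9.8% instead of 7.4%. This overstates the effect of planned draws, because the total includes screening draws and those made after the Day 14 sample. A smaller blood volume would raise f in proportion. Within a cohort both arms follow the same schedule, so most of the bias cancels in the comparison.

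**The case against.** The protocol does point to a calculation, and its section 14.7.1 refers back to where the citation stands. A missing citation in the SAP does not show that the endpoint changed. The contents of references 22 and 23 are not in the documents, and Protocol 10.1.1.1 ties the cited assumptions to all four markers. Making two of them supportive is therefore a choice, and no section states constant circulating hemoglobin. Protocol 4.2.3 accepts concentrations as an indirect gauge of plasma-volume change and warns that blood sampling may make them more variable. Table 6 plans 12 tracer samples for each of about 64 patients, so the group without tracer may be small. Protocol 14.7.2 makes the primary pharmacodynamic analysis descriptive, and 14.7.3 calls the ANCOVA exploratory.

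Much of this stands, and it rules out two stronger readings. A reader might infer that the indirect method can never yield a plasma-volume change; Protocol 10.1.1.1, 10.1.2 and 10.1.2.1 say otherwise. A reader might also infer that the plan runs four separate tests. No section says so. The figure for that case, 1 - 0.95^4 = 18.5% if independent and between 5% and 18.5% if positively correlated, applies only if four models were run and the best one selected. SAP 2.6.2 openly disclaims multiplicity control because the study is exploratory.

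The two gaps remain. An exploratory aim explains the lack of alpha control, but not an undefined outcome in what the SAP calls its primary analysis, nor a covariate that some patients are allowed not to have.

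**Conclusion.** The point holds as a gap in specification with a concrete consequence. SAP 2.6.1 does not carry forward the calculation that the protocol points to, so the outcome in SAP 2.6.2 has no formula or unit. If the covariate is the tracer plasma volume, every patient without a Day 1 tracer test is lost from the hemoconcentration model. The number lost cannot be derived from the documents; it could be zero if Table 6 is fully realised. The missing adjustment for the outcome's own baseline affects all patients. Under randomization it does not bias the comparison in expectation, but it can cost precision and leaves chance imbalance in that baseline unadjusted.

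The conclusion rests on two assumptions: that baseline plasma volume means the tracer value, and that missing covariates are handled by complete-case fitting. The 7.4% example shows the arithmetic and is not a predicted effect.

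**What to change.** In SAP 2.6.1, name one indirect variable for all patients: percent change in plasma volume = 100 x [(Hb1/Hb14) x (1-Hct14)/(1-Hct1) - 1]. State its unit and its assumption of constant circulating hemoglobin. Protocol 4.2.3 expects erythropoiesis to need 4-8 weeks to become detectable, which supports that assumption over 14 days. If the sponsor intends a different calculation, or one that uses albumin and total protein, the SAP should write that out instead.

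In SAP 2.6.2, keep the fixed terms but replace baseline plasma volume with baseline hematocrit or hemoglobin in this model. Keep the tracer baseline for the tracer model. Report the four markers as supportive.

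In SAP 2.2.1, make clear that the pharmacodynamic population is determined variable by variable. If it required valid values of both main parameters, it would exclude the same patients before any model was fitted.

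The cost is SAP wording and one derived variable. Hemoglobin and hematocrit are already scheduled for all patients on Days 1 and 14 (Protocol 10.1.2 and Table 3), so no sample or visit is added. Two things are given up: single-marker results become supportive, and the derived value is sensitive to blood loss from sampling.
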